9.7.1.8.4 VITAL SIGNS

Descriptive statistics for vital signs parameters (ie, systolic and diastolic BP, pulse, respiratory rate, temperature, weight), and changes from baseline will be presented by visit and treatment group.

9.7.1.8.5 ELECTROCARDIOGRAMS

Descriptive statistics for ECG parameters and changes from baseline will be presented by visit and treatment group. Shift tables will present changes from baseline in ECG interpretation (categorized as normal; abnormal, not clinically significant; and abnormal, clinically significant) to the end of treatment.

In addition, the number (percentage) of subjects with at least 1 postbaseline abnormal ECG result in QTcF during the treatment period will be summarized. Clinically abnormal ECG results in QTcF will be categorized as follows:

Absolute QTc interval prolongation:

- QTc interval >450 msec
- QTc interval >480 msec
- QTc interval >500 msec

Change from baseline in QTc interval:

- QTc interval increases from baseline >30 msec
- QTc interval increases from baseline >60 msec

9.7.1.8.6 OTHER SAFETY ANALYSES

Cognitive decline will be assessed as a safety assessment, in addition to efficacy assessments. Cognitive assessments will include the ADAS-cog₁₄, MMSE, CDR, and CBB (see [Section 9.7.1.6](#)).

9.7.2 Determination of Sample Size

9.7.2.1 Sample Size Rationale in the MCI/Prodromal Cohort

Primary endpoint – derived ADCOMS

The sample size and design characteristics to test the hypothesis for the primary objective based on the primary endpoint, change from baseline of the derived ADCOMS at 18 months, were determined by means of simulations. Extensive study simulations have shown that a total of 500 subjects will be sufficient to demonstrate that the most likely ED₉₀ dose achieves a 25% improvement over placebo with a probability of at least 80% in the interim and final analyses. There is at least a 90% probability of study success for the dose response scenarios where treatment was considered to have a clinically meaningful treatment effect. Simulations have also shown that if there is no obvious dose effect, the probability of falsely claiming superiority to placebo is at most 5%.

For each of the 4 treatment groups (3 active doses and placebo) the final number of subjects per group will differ depending on the observed interim treatment responses. The simulation plan will be an appendix to the statistical analysis plan and will present further details.

vMRI

The null hypothesis is that there is no difference between active dose and placebo. There are 3 null hypotheses corresponding to 3 active doses. The alternative hypothesis is that at least 1 null hypothesis is false (1-sided). The null hypotheses will be tested using Dunnett's method with 1-sided alpha of 0.05. The statistical power was estimated through simulation for a moderate dose-response assumption that the percent reduction in change from baseline of total hippocampal volume compared with placebo would be 15%, 20%, and 25% corresponding to the 3 doses, respectively. The estimated power for the actual planned study sample size is 78% at 18 months assuming an attrition rate of 20% at 18 months. Under a stronger dose-response assumption (ie, the percent reduction in change from baseline of total hippocampal volume compared with placebo is twice as much as that in the moderate dose-response assumption), the estimated power is at least 99% at 18 months.

Amyloid PET

The null and alternative hypotheses and the statistical test are the same as those for vMRI. To estimate the sample size for the amyloid PET imaging subgroup at 18 months, a common SD of the change from baseline was estimated at 0.33 and a reasonable mean difference between treatment and placebo was estimated as 0.25 (standardized uptake value ratio [SUVR]). Assuming a moderate dose-response, the best dose would achieve a difference of 0.25 (SUVR) and the middle and low doses would achieve a difference of 0.2 and 0.15 (SUVR), respectively; this would require a total of 100 subjects from all 4 arms at 18 months to achieve 80% power.

9.7.2.2 Sample Size Rationale for the Mild to Moderate AD Cohort (revised per Amendment 01)

ADCOMS at Month 18

The null hypothesis is that there is no difference between active dose and placebo. There are 2 null hypotheses corresponding to 2 active doses. The alternative hypothesis is that at least 1 null hypothesis is false. The null hypotheses will be tested using Dunnett's test with 2-sided alpha of 0.05 as described for the Mild to Moderate AD cohort in [Section 9.7.1.6.2](#). The statistical power was estimated through simulation for the dose-response assumption that the percent reduction in change from baseline of ADCOMS at 18 months compared with placebo would be 33% and 50% corresponding to the 2 doses, respectively. The estimated power for the actual planned 200 mild to moderate AD subjects is approximately 80% assuming a 2-sided alpha of 0.05. (revised per Amendment 01)

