9.7 Statistical Methods

All statistical analyses will be performed by the sponsor or designee. Statistical analyses will be performed using SAS software or other validated statistical software as required.

All statistical tests will be based on the 5% (2-sided) level of significance, except for the Bayesian methods on the primary endpoint.

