9.7.1.6.2 SECONDARY EFFICACY ANALYSES

The MCI/Prodromal Cohort

An MMRM will be used to analyze the following secondary endpoints:

- Change from baseline in total hippocampal atrophy at 12 and 18 months of treatment in MCI/Prodromal subjects as measured by vMRI
- Change from baseline in CSF $A\beta(1-x)$ after 4 weeks and 18 months of treatment in MCI/Prodromal subjects. Data from early discontinuations will also be included.

Comparisons between each treatment group and placebo will be performed.

The Mild to Moderate AD Cohort (revised per Amendment 01)

The MMRM will be used to analyze the change from baseline of derived ADCOMS at 18 months in mild to moderate AD. If there is no treatment group-by-population interaction in the overall study, the MMRM analysis will include all subjects (MCI/Prodromal or mild to moderate AD) in the overall study. Otherwise, the MMRM analysis will only include subjects in the Mild to Moderate AD cohort. The comparison between placebo and active doses will be performed within mild to moderate AD subjects regardless of subjects included in the MMRM analysis. Dunnett's method will be used to control for multiplicity due to multiple comparisons. (revised per Amendment 01)

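### The protocol sets vMRI and amyloid PET tests at one-sided 5% in Section 9.7.2.1 but all non-Bayesian tests at two-sided 5% in Section 9.7; the stated 78% and 80% powers hold only on the one-sided reading

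*Protocol*

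**What the plan says.** Section 9.7 lays down one rule for the whole study: "All statistical tests will be based on the 5% (2-sided) level of significance, except for the Bayesian methods on the primary endpoint". The synopsis repeats it under Statistical Methods.

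Section 9.7.2.1 then prescribes, for hippocampal volume by vMRI (a secondary endpoint), Dunnett's "method with 1-sided alpha of 0.05. The statistical power was estimated through simulation for a moderate dose-response assumption". The assumed effects are stated as follows: "the percent reduction in change from baseline of total hippocampal volume compared with placebo would be 15%, 20%, and 25% corresponding to the 3 doses". The result given is: "The estimated power for the actual planned study sample size is 78% at 18 months assuming an attrition rate of 20% at 18 months". The amyloid PET paragraph, for an exploratory endpoint, adopts the same hypotheses and test. With an SD of 0.33 and differences of 0.15, 0.20 and 0.25 SUVR it concludes: "this would require a total of 100 subjects from all 4 arms at 18 months to achieve 80% power". The synopsis carries both paragraphs as well.

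Section 9.7.1.6.2 gives an MMRM for the MCI/Prodromal secondary endpoints and adds only: "Comparisons between each treatment group and placebo will be performed". Section 9.7.1.6.3 does much the same for PET with a linear mixed model. Neither names Dunnett or a one-sided test for these endpoints. For the mild to moderate AD cohort, by contrast, Section 9.7.1.6.2 names Dunnett and Section 9.7.2.2 computes power at two-sided 0.05.

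**The concern.** The only exception to the two-sided rule is the Bayesian analysis of the primary endpoint. vMRI and PET are neither Bayesian nor primary, so a one-sided 5% test for them conflicts with Section 9.7. Both statements are phrased as what will be done, so a later analysis plan can follow one only by departing from the other.

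Two things depend on the answer. The first is the power a reader believes these endpoints have. The second is the threshold for calling a dose positive. With 25 per arm, a dose whose Dunnett statistic falls between about 2.09 and 2.39 would succeed under Section 9.7.2.1 and fail under a two-sided Dunnett test. Section 9.2.5.4 offers slowed hippocampal atrophy as support for disease modification. A threshold chosen after unblinding would therefore be open to challenge.

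**Working it through.** **Set-up.** Each of three doses is compared with a shared placebo using a pooled variance. Power is the chance of at least one rejection, which matches the alternative hypothesis in Section 9.7.2.1. With n per arm, each statistic has noncentrality difference / (SD × √(2/n)) and 4n − 4 degrees of freedom. Critical values and powers come from simulation with at least 400,000 replicates.

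**Amyloid PET (all inputs printed in Section 9.7.2.1).**
- n = 100/4 = 25 per arm; SD 0.33; differences 0.15, 0.20 and 0.25; 96 degrees of freedom.
- Standard error: 0.33 × √(2/25) = 0.0933.
- Noncentralities: 0.15/0.0933 = 1.61; 0.20/0.0933 = 2.14; 0.25/0.0933 = 2.68.
- One-sided 5% Dunnett, critical value about 2.09: power 81%. This reproduces the stated 80%, so that figure does rest on the one-sided test.
- Two-sided 5% Dunnett, critical value about 2.39: power 71%.
- Size needed for 80% with the two-sided test: 30 per arm gives about 79%, and 31 per arm (124 in total) gives about 81%.

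**vMRI (back-calculated).** The protocol gives neither an SD nor a placebo decline, so the 78% cannot be reproduced independently. I solved for the effect size that yields it.
- Completers: 500 × 0.80 = 400, or 100 per arm if the arms are equal.
- With effects in the ratio 15:20:25, one-sided Dunnett (critical value about 2.07) gives 78% when the top-dose effect is 0.359 SD. The noncentralities are then 0.359/√(2/100) = 2.54 for the top dose, and 2.03 and 1.52 for the other two.
- Two-sided Dunnett (critical value about 2.36), same effects: power 67%.
- Adaptive randomization will make the arms unequal. Recalibrating with completers of 160/80/80/80, 160/40/40/160 and 150/50/50/150 (placebo first) gives 67.0% to 67.7%.
- If the 78% meant power for the best dose alone, the two-sided figure would be 68% to 69%.
- Doubling the effects, as in the stronger scenario, leaves two-sided power above 99%.

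**The three readings side by side.**

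| Reading | vMRI | PET, 25 per arm |
|---|---|---|
| One-sided 5% Dunnett (Section 9.7.2.1) | 78% (calibrated) | 81% |
| Two-sided 5% Dunnett (Section 9.7 rule, Dunnett kept) | 67% | 71% |
| Two-sided 5%, no multiplicity adjustment | 81% | 84% |

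**The case against.** The best reply is that Section 9.7.2.1 does more than assume a test: it says how the hypotheses will be tested. If that specific sentence overrides the general rule, nothing is miscalculated. The PET figure reproduces and the vMRI figure cannot be faulted. This stands to the extent that 67% and 71% are conditional. A reader might infer that the trial simply delivers those powers, but no single passage prescribes a two-sided Dunnett test for these endpoints. That test comes from combining the general rule with the multiplicity method in the sample size section. The reply does not remove the conflict, because Section 9.7 allows no such override.

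A reader might also infer that the family-wise error is uncontrolled, since Section 9.7.1.6.2 names no adjustment for this cohort. Three unadjusted two-sided 5% comparisons against a shared placebo would indeed have a family-wise error of about 12.5%. But the section does not say that the comparisons are unadjusted, Section 9.7.2.1 does name Dunnett, and further detail may properly sit in the statistical analysis plan. That error also belongs to the third row of the table, where power is higher than stated. It cannot be charged to the protocol together with the power loss in the second row.

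Three smaller points are fair. Twenty-five PET scans per arm is a minimum for each ligand (Section 9.2.5.3), so the final number may be larger and 71% is power at the planned 100. The vMRI figure is inferred from the stated one. And Listing 2 in one copy of Appendix 2 carries Amendment 02 text, while the Section 9.7 supplied is the Amendment 01 version. A later version may have settled the matter, although the synopsis of the version before Amendment 01 shows the same mismatch.

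**Conclusion.** The contradiction is real and the protocol does not resolve it. The stated powers of 78% and 80% rest on a one-sided 5% Dunnett test that the study-wide rule does not allow for these endpoints.

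If the two-sided rule governs and Dunnett is retained, PET power at 100 subjects is about 71%. That figure follows directly from printed inputs. On the same condition vMRI power is about 67%, which rests on taking the stated 78% as correct any-rejection power with 20% attrition. If the one-sided sentence is meant to govern, the powers can stand, but Section 9.7 and the synopsis are then wrong as written.

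The weight is moderate. The endpoints are secondary and exploratory, and the Bayesian primary analysis does not depend on them. It should still be settled before unblinding, because it fixes both a decision threshold and two published power figures.

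**What to change.** Preferred: name Dunnett's method at two-sided 5% for the MCI/Prodromal vMRI comparisons in Section 9.7.1.6.2 and for PET in Section 9.7.1.6.3. This agrees with the general rule and with the AD cohort. Replace the one-sided wording in Section 9.7.2.1 and the synopsis, and restate power as about 67% for vMRI and about 71% for PET with 100 subjects. The sponsor should rerun the vMRI simulation with its own SD and placebo decline and print those inputs.

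Alternative: keep the one-sided test, write an explicit and justified exception for these two endpoints into Section 9.7 and the synopsis, and name the one-sided Dunnett test in the analysis sections.

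The cost is wording in the protocol and analysis plan and, on the preferred route, two less favourable power figures. No extra subjects are required. Only if 80% is wanted for PET under the two-sided test would the scan target rise, to about 31 per arm (124 in total).

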9.7.3 Interim Analysis

An interim safety analysis will be conducted when the first 60 subjects have completed 12 weeks of treatment (or discontinue study drug early) in Stage A. (revised per Amendment 01)

The MCI/Prodromal Cohort

The Bayesian interim analyses and response adaptive randomization will be conducted by an unblinded external independent analysis group in accordance with the protocol. Oversight of the Bayesian interim analyses and response adaptive randomization will be conducted by an independent unblinded committee that has expertise with Bayesian adaptive design in clinical studies to ensure that the response adaptive randomization process and interim analyses perform as expected. The analysis group will provide the interim analysis outcomes to the committee at each interim analysis. The committee will ensure the integrity of the interim analysis and response adaptive randomization process through review of efficacy data. In addition, the committee will act in an independent advisory capacity to monitor the Bayesian interim analysis outcomes according to the early success and futility boundaries prespecified in the protocol. The committee will not be charged with any subject safety issues; this will remain the responsibility of the DSMB.

If the predefined early success criteria are met during the recruitment period, further recruitment and enrollment of MCI/Prodromal subjects into the study will stop (following confirmation from the Sponsor's Senior Management) and all currently randomized subjects will complete the full 18 months of treatment. No further interim analyses will be conducted after achieving early success.

If the predefined threshold for futility is reached, no additional subjects will be randomized into the study and the treatment of subjects already randomized into the study will stop and the study will be declared as "failed". All subjects will be monitored for safety for 3 months following their last dose.

If neither early success nor futility is reached and the study reaches full randomization, all subjects will complete 18 months of treatment. Interim efficacy analyses will be conducted every 3 months after full randomization is reached to assess futility and early success until all subjects complete 18 months of treatment. After full randomization, all study subjects will stop treatment only in the event of futility.

The DSMB will continue to monitor the safety aspects of the study throughout Stage A and Stage B. Details will be provided in the DSMB Charter. The study may be stopped for safety at any time.

The first Bayesian adaptive interim analysis will be conducted when 100 MCI/Prodromal subjects have been randomized into the study (ie, including MCI/Prodromal subjects from Stage A and Stage B). (revised per Amendment 01) Further interim efficacy analyses will be conducted after each additional 50 MCI/Prodromal subjects have been randomized, to a maximum of 500 MCI/Prodromal subjects (ie, at 100, 150, 200, 250, 300, 350, 400, 450, 500 subjects randomized). If the study reaches full randomization, additional interim analyses will be conducted every 3 months until all subjects complete 18 months of treatment. The study will be monitored for futility at each interim analysis. Starting at the interim analysis for 200 subjects, the study will be monitored for success at each interim analysis. Each interim analysis will be conducted on data for the derived ADCOMS.

In addition, at each interim efficacy analysis, response adaptive randomization will be used to update the allocation of new subjects between placebo and active doses according to a predefined automated algorithm.

The Mild to Moderate AD Cohort (revised per Amendment 01)

A group sequential design will be used for the Mild to Moderate AD cohort. (revised per Amendment 01) This design includes 3 looks, 2 interim looks (when 60% and 80% information fractions are achieved) and 1 final look. The information fraction is the number of assessments in all treatment arms divided by the total number of expected assessments. Interim analyses will be performed after the MCI/Prodromal cohort crosses the early success boundary. The corresponding efficacy boundaries will be 0.076, 0.022, and 0.0423 for the first, second, and final analyses, respectively. If the actual information fraction during the interim analyses is different from 60% or 80% at the interim, the efficacy boundaries will be adjusted based on the actual information fraction.

If early success in the MCI/Prodromal cohort is not achieved before the final analysis that is performed when all subjects have completed 18 months treatment, then only a final analysis will be performed in mild to moderate AD subjects. In the event of futility in the MCI/Prodromal cohort, an analysis will be performed for the Mild to Moderate AD cohort based on the data for mild to moderate AD subjects available at that time. (revised per Amendment 01)

Randomization into the Mild to Moderate AD cohort will remain at a fixed schedule throughout Stage B. (revised per Amendment 01)

The interim analyses in the Mild to Moderate AD cohort will be conducted by an independent analysis group. (revised per Amendment 01)

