All mild to moderate AD subjects will be included in the efficacy evaluations of the Mild to Moderate AD cohort. The analysis of the Mild to Moderate AD cohort is based on the group sequential design. Interim analyses in the Mild to Moderate AD cohort will only be performed after the MCI/Prodromal cohort crosses the early success boundary. The early efficacy signal based on the change from baseline of ADCOMS at 18 months is defined as crossing the interim-analysis boundaries for overwhelming efficacy in the mild to moderate AD population. The O'Brien-Fleming (OF) boundaries based on Lan-DeMets alpha spending function will be used to assess overwhelming efficacy. The corresponding OF boundaries based on *P* values will be 0.076, 0.0221, and 0.0423 for the first, second, and final analyses, respectively, according to 2 planned interim analyses at the 60% and 80% information fraction. (revised per Amendment 01)

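### The AD cohort's information fraction is not tied to the 18-month outcome; read literally it overstates information at both interim looks, with modest type I error inflation

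*Protocol*

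**What the plan says.** Section 9.7.3 sets a group sequential design for this cohort: "This design includes 3 looks, 2 interim looks (when 60% and 80% information fractions are achieved) and 1 final look". It then defines the scale: "The information fraction is the number of assessments in all treatment arms divided by the total number of expected assessments". Departures from plan are handled on the same scale: "If the actual information fraction during the interim analyses is different from 60% or 80% at the interim, the efficacy boundaries will be adjusted".

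Section 9.7.1.6 ties the looks to one time point: "The early efficacy signal based on the change from baseline of ADCOMS at 18 months is defined as crossing the interim-analysis boundaries for overwhelming efficacy". It adds that O'Brien-Fleming "boundaries based on Lan-DeMets alpha spending function will be used to assess overwhelming efficacy". Section 9.7.1.6.2 makes the analysis an MMRM, and Section 9.7.2.2 states two null hypotheses, one per active dose, at a 2-sided alpha of 0.05.

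ADCOMS components are collected on treatment at Months 3, 6, 9, 12, 15 and 18 (Visits 11 and 14 to 18, Table 7), and again at Months 19 and 21 after treatment. Some AD subjects may be randomized to 5 mg in Stage A (Section 9.7.4). The interim looks occur only after early success in the MCI/Prodromal cohort.

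**The concern.** An alpha-spending boundary is valid when the fraction used to compute it reflects the information on the tested contrast, because that fraction fixes both the alpha released and the assumed correlation between looks. Here the fraction can rise with no gain in 18-month outcomes. A subject who has reached Month 12 has supplied 4 of 6 assessments (67%) and no 18-month value. If Months 19 and 21 count, a subject at Month 15 has supplied 5 of 8 (62.5%), again with none.

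The adjustment rule cannot repair this. A look taken at 60% of assessments registers as on schedule and keeps the 60% boundary.

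At stake are an interim efficacy signal based on little 18-month data and a type I error somewhat above the stated 5%.

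**Working it through.** **1. The plan's boundaries.** O'Brien-Fleming-type spending, two one-sided tests at 0.025: α(t) = 4·[1 − Φ(z₀.₉₈₇₅/√t)]. Cumulative spend at t = 0.6, 0.8, 1 is 0.0076, 0.0244, 0.0500. The critical values are z = 2.669, 2.289, 2.031, so nominal P is 0.0076, 0.0221, 0.0423. The second and third match Section 9.7.1.6: "0.076, 0.0221, and 0.0423 for the first, second, and final analyses, respectively". The first does not: both sections print 0.076. That is a separate and larger error (overall type I error about 9.7% as printed, even at true fractions of 0.6 and 0.8). The rest of this check uses 0.0076, taken to be the intended value.

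**2. Inputs.**
- From the protocol: six on-treatment visits; up to 200 subjects; Stage B of about 42 months (Synopsis).
- Assumed: uniform accrual over R = 42 − 18 (treatment) − 3 (follow-up) − 2 (screening) = 19 months; no dropout. Other values of R are tried below.

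**3. When does the count reach 60% and 80%?** At calendar time T the share of subjects who have reached visit v is min(1, (T − v)/R). The all-assessments fraction is the mean of this over v = 3, 6, 9, 12, 15, 18.
- T = 21.9: (0.995 + 0.837 + 0.679 + 0.521 + 0.363 + 0.205)/6 = 0.60. The 18-month share is 20.5%, about 41 of 200.
- T = 26.8: (1 + 1 + 0.937 + 0.779 + 0.621 + 0.463)/6 = 0.80. The 18-month share is 46.3%, about 93 of 200.

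**4. Credit for earlier visits.** The MMRM uses partial records, so the completer share understates information. With w_k the share of subjects observed through visit k and Σ_k the covariance of their first k visits, A = Σ w_k Σ_k⁻¹ (each term padded with zeros to 6×6), and the Month-18 fraction is σ²₁₈/[A⁻¹]₆₆. Models tried: AR(1) with 0.5, 0.7 and 0.9 per visit, compound symmetry with 0.5 and 0.7, and random slope. AR(1) 0.5 and 0.9 gave the lowest and highest values:

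| Accrual (months) | 18-month share at nominal 60% / 80% | MMRM information at nominal 60% | MMRM information at nominal 80% |
|---|---|---|---|
| 12 | 2.5% / 35% | 0.03–0.11 | 0.40–0.68 |
| 19 | 20.5% / 46% | 0.23–0.46 | 0.50–0.74 |
| 24 | 29% / 51% | 0.32–0.53 | 0.55–0.76 |
| 36 | 39% / 59% | 0.41–0.58 | 0.62–0.79 |

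Month-18 information is below the nominal fraction in every case. At 36 months with high correlation the gap nearly closes (0.58 against 0.60).

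**5. Effect on alpha.** At 19-month accrual, spending at the true first-look information would be about 0.000007 (t = 0.234) to 0.0019 (t = 0.458), against 0.0076. Type I error is the probability that a trivariate normal with correlations √(tᵢ/tⱼ), at the true fractions, crosses ±2.669, ±2.289 or ±2.031:
- planned fractions (0.6, 0.8, 1): 5.0%
- 19 months, AR(1) 0.5 (0.234, 0.501, 1): 6.0%
- 19 months, AR(1) 0.9 (0.458, 0.737, 1): 5.3%
- 12 to 36 months, all correlation models: about 5.1% to 6.4%

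**The case against.** The strongest reply is that the visit was understood. The looks concern the 18-month change, the cohort's sample-size rationale is headed with Month 18, and the word for all in the definition attaches to the arms, not to the visits. If only 18-month assessments were meant, the problem disappears. This is a fair reading, but it is not written, and whoever runs the looks would have to choose between two counts that lead to different look dates and different alpha. The protocol fixes this definition itself, so it is not a detail merely left to the SAP.

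Other points stand and limit the finding:
- The looks happen only after MCI/Prodromal early success, and may then fall later than the nominal fractions.
- Uniform accrual ignores the Stage A block and the pause before Stage B. With 20 to 45 AD subjects in Stage A (an assumption) and 19 to 24 months of Stage B accrual, the 18-month share at a nominal 60% is 24% to 33%, and type I error 5.1% to 5.9%.
- The 5 mg effect is small. Stage A targets 15 subjects per arm over both cohorts, so at most about 15 of 200, and they enter numerator and denominator alike.
- Dunnett's adjustment for two doses is not modelled.
- This is a secondary endpoint in Phase 2. Crossing is called an early efficacy signal, no stopping of treatment is attached to it, and allocation stays fixed.

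A reader might infer that information is always grossly overstated, that error reaches 6.5%, or that the proper first boundary is near 0.000001. The documents do not support these. The 6.5% comes from 12-month accrual counting completers only, and the 0.000001 from 19-month accrual counting completers only. Both ignore what the planned MMRM recovers from earlier visits.

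**Conclusion.** The point holds as a defect in a stated definition. Taken literally, the fraction overstates Month-18 information at both looks in every accrual and correlation case tried, and the adjustment rule carries the same error. Type I error for a single comparison is about 5.3% to 6.0% at 19-month accrual, and about 5.1% to 6.4% over 12 to 36 months. That is modest. It is conditional on the looks taking place, on the first boundary being 0.0076, and on no dropout. The size cannot be fixed more closely, because the protocol gives neither accrual nor within-subject correlation for this cohort. The more tangible consequence is an overwhelming-efficacy signal that could rest on about 41 of 200 subjects with 18-month data while the boundary presumes 60% information. The definition should be corrected before any look.

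**What to change.** Replace the sentence in Section 9.7.3. Define the information fraction as the number of mild to moderate AD subjects in the placebo, 15 mg and 50 mg arms with an observed 18-month ADCOMS, divided by the number planned. Alternatively, use the ratio of inverse variances of the Month-18 contrast from the MMRM. State that the looks are timed, and the boundaries recomputed, on that scale.

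The cost is later looks. With 19-month accrual, 60% and 80% of 18-month outcomes fall at 18 + 0.6 × 19 = 29.4 and 18 + 0.8 × 19 = 33.2 months, instead of 21.9 and 26.8: delays of about 7.5 and 6.4 months. The inverse-variance version credits partial records and would delay the looks less. If Month 18 was always intended, the edit costs nothing. The first boundary printed as 0.076 needs its own correction in the same paragraph and in Section 9.7.1.6.
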